### 3.1 INCLUSION CRITERIA

1. Age  $\geq$ 18 years
2. Stage 3 acute kidney injury according to the KDIGO criteria
3. Started or intending to start CKRT for volume management
4. Attending intensivist or nephrologist intending to remove net fluid using CKRT for at least 48 hours

### 3.2 EXCLUSION CRITERIA

1. Respiratory distress due to pulmonary edema or fluid overload
2. Massive volume infusion (*i.e.*,  $>200$  mL/h for  $>6$  hours of continuous infusion)
3. No intention to remove net fluid as determined by attending intensivist or nephrologist
4. Attending intensivist or nephrologist believes that the protocol will not be followed
5. Continuous net fluid removal for  $>24$  hours prior to study enrollment
6. Body Mass Index  $>40$
7. Patients on chronic outpatient hemodialysis
8. Patients with history of, or current admission for kidney transplantation
9. Patients with comfort measures only orders (*i.e.*, CMO)
10. Moribund not expected to survive  $>24$  hours
11. Confirmed pregnancy
12. Patients treated with extracorporeal membrane oxygenation (ECMO), ventricular assist device (VAD), or intra-aortic balloon pump (IABP)
13. Organ donors with neurological determination of death (*i.e.*, brain dead donors)
14. Drug overdose requiring CKRT for drug clearance
15. Enrollment in a concurrent interventional clinical trial with direct impact on fluid balance (*e.g.*,  $>500$  mL study drug administration)

### 3.3 ASSESSING ATTENDING PHYSICIAN EQUIPOISE

After meeting inclusion and none of the exclusion criteria, the attending intensivist or nephrologist will be asked twice daily if she/he strongly believed:

- a) emergent and rapid fluid removal should occur

OR

- b) fluid removal should be deferred

If the answer is negative to both questions, the patient will be considered fully eligible and efforts to obtain informed consent from patient or LAR will commence. If a patient's eligibility is excluded by an attending physician, the patient will be reconsidered for participation in the trial, and the physician will be re-approached later, provided the patient still meets inclusion criteria and none of exclusion criteria.

### 3.4 STUDY INITIATION TIME WINDOW

All patients will be consented and enrolled within 48 hours of meeting full eligibility. Time of signing the informed consent will be the study enrollment time. Once enrolled, the assigned intervention must be initiated within 24 hours.

### 3.5 OUTCOMES

#### 3.5.1 PRIMARY OUTCOMES

1. Mean delivered  $UF_{NET}$  rates
2. No. of participants with protocol deviation
3. Patient recruitment rate.

#### 3.5.2 SECONDARY OUTCOMES

1. Daily fluid balance
2. Cumulative fluid balance
3. Duration of kidney replacement therapy
4. Duration of mechanical ventilation
5. Organ failure free days
6. ICU length of stay
7. Hospital length of stay
8. Hospital mortality
9. Dialysis dependence at hospital discharge

#### 3.5.3 SAFETY OUTCOMES

1. No. of intradialytic hypotensive episodes
2. No. of intradialytic hypertensive episodes
3. No. of intradialytic new onset cardiac arrhythmias including supraventricular tachycardia, bradycardia, atrial fibrillation, ventricular tachycardia, ventricular fibrillation, and cardiac arrest
4. No. of participants with emergent use of rescue  $UF_{NET}$  with rates higher than the assigned treatment arm
5. No. of participants with severe hypophosphatemia ( $<0.5$  mg/dL)
6. No. of participants with severe hypokalemia ( $<3.0$  mg/dL)
7. No. of participants with severe hypocalcemia ( $<1.90$  mg/dL or ionized calcium  $<0.90$  mmol/L)
8. No. of episodes of stopping CKRT due to filter clotting or clogging
9. No. of participants with discontinuation of  $UF_{NET}$  due to hemodynamic instability
10. No. of participants in whom surgical wounds are left open due to edema
11. No. of participants with new organ dysfunction
12. No. of participants with worsening of systolic or diastolic cardiac function on echocardiogram
13. No. of participants with worsening of pulmonary edema on chest X Ray and/or CT scan
14. No. of participants with worsening of ileus on abdominal X Ray and/or CT scan
15. No. of participants with bowel ischemia or anastomotic breakdown based on intraoperative findings
16. No. of participants with pressure ulcerations
17. No. of participants with new wound infections
18. No. of participants with new arterial or venous thrombosis
19. No. of participants with severe anemia requiring red cell transfusions

20. No. of participants with severe thrombocytopenia requiring platelet transfusions
21. No. of participants with new secondary infections

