### 5.3.2 POTENTIAL DISADVANTAGES

Restrictive UFNET rate strategy may theoretically be associated with longer tissue exposure to fluid overload and may increase time to achieving euvolemia. Prolonged exposure to fluid overload may impair kidney recovery, prolong the duration of kidney replacement therapy, or increase ventilator dependence. However, the risks of prolonged exposure to FO associated with restrictive UFNET rate strategy must be balanced against the risk of ischemic organ injury due to hypotensive episodes and blood pressure variability associated with faster and more liberal UFNET rates used in clinical practice.

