## F2. CKRT DATA COLLECTION

Measurement/ Event	Initiation of RRT	Baselin e/Day 0@	1	2	3	4	5	6	7	8-14	15-21	22-28
Indication for KRT - Volume status - Serum potassium - Acid-base status - Symptoms - BUN - Hemodynamic status	X											
CKRT - Mode - Hemodiafilter - Blood flow rate - Dialysate flow rate - Replacement fluid rate - Ultrafiltration rate - Net Ultrafiltration rate - Hours of therapy - 24- hour effluent volume - Anticoagulation		X	X	X	X	X	X	X	X	X	X	X
Complications - Clogging - Clotting - Downtime		X	X	X	X	X	X	X	X	X	X	X

Measurement/ Event	Initiation of RRT	Baseline e/Day 0@	1	2	3	4	5	6	7	8-14	15-21	22-28
- Discontinuation of UF NET due to patient instability												
Indications for termination of KRT		X	X	X	X	X	X	X	X	X	X	X

@= Data collected before initiation of study intervention

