### 4.2.2 PROTOCOL ADHERENCE

We have defined protocol deviation *a priori* as delivered UFNET rate that lies  $>0.5$  mL/kg/h outside of the target UFNET rate range in the assigned treatment group for greater than six consecutive hours during fluid removal *without* significant changes in MAP (*i.e.*, MAP  $< 65$  mmHg or  $\geq 90$  mmHg). As such, out of range UFNET rates  $>0.5$  mL/kg/h beyond the target UFNET rate range in the assigned treatment group will not constitute a protocol deviation when the bedside team titrated the UFNET rate as required to manage the patient hemodynamics (*i.e.*, when clinicians appropriately decreased rate or stopped fluid removal for hypotension; increased fluid removal rate for hypertension or for treatment of respiratory distress due to fluid overload and pulmonary edema).

We will report the following stratified by restrictive and liberal UFNET rate groups: i.) no. of occurrences of deviations for six consecutive hours divided by UFNET days (mean events per day); ii.) no. of days with UFNET out of range for at least six consecutive hours; iii.) no. of patients with at least one occurrence of UFNET rate out of range for six consecutive hours. The proportion of patients with protocol deviation will be compared using the Wald test for GLMM and adjusted for prespecified covariates.

As an exploratory analysis, we will also report the proportion of total hours of UFNET rate within, above, or below range for each patient weighted equally and proportionally to total hours of fluid removal.

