### 4.3 ANALYSIS METHODS FOR SECONDARY AND SAFETY OUTCOMES

We will use GLMM regression after adjusting for various prespecified variables. We will consider observed differences between groups to be statistically significant at a two-sided, nominal alpha of 0.05 for all outcomes.

For binary outcomes, we will use the Wald test for GLMM to compare the proportion of patients in the two UFNET rate groups (Appendix A).

For continuous variables, we will report incident rate ratios calculated with zero-truncated negative binomial regression modeling adjusted for prespecified baseline covariates.

For independence from KRT and hospital mortality, we will fit GLMM regression models and report odds ratios with corresponding 95% confidence intervals from logistic regression after adjusting for prespecified baseline covariates. To safeguard against erroneous type I error inflation in secondary outcomes, we will apply the conservative Hochberg procedure for adjustment on multiplicity to two key secondary outcomes of mortality and KRT dependence. Because of the potential for type I error due to multiple comparisons, findings for analyses of the other secondary end points will be interpreted as exploratory.

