5.3.3 TABLE 3: SAFETY OUTCOMES

Safety Outcomes	Restrictive		Liberal		Unadjusted P value	Adjusted P value §
	No. of Patients (%)	No. of episodes	No. of Patients (%)	No. of episodes		
Intradialytic hypotension						
Intradialytic hypertension						
Cardiac arrhythmias						
Use of rescue net ultrafiltration						
Hypophosphatemia (<0.5 mg/dL)						
Hypokalemia (<3.0 mg/dL)						
Hypocalcemia (<1.90 mg/dL)						
Hemofilter clotting or clogging						
UF NET discontinuation due to instability						
Surgical wounds edema						
New organ dysfunction						
Worsening cardiac function						
Worsening of pulmonary edema						
Worsening of ileus						
Bowel ischemia or anastomotic breakdown						
New pressure ulcerations						
New wound infections						
New arterial or venous thrombosis						
Severe anemia						
Severe thrombocytopenia						
New secondary infections						

§ Adjusted for differences in age, baseline eGFR, APACHE-III score, Elixhauser Comorbidity Index score, mechanical ventilation, admission source, percentage of fluid overload, sepsis, and baseline cardiovascular SOFA score. P values are for the between-group differences in the percentage of patients with a specific event and have not been adjusted for multiple comparisons.

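### Four episode-count safety outcomes have no time-on-CKRT denominator and three differing analyses, so the comparison tilts against whichever arm stays on CKRT longer

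*SAP*

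**What the plan says.** SAP 3.5.3 lists 21 safety outcomes. Seventeen are numbers of participants. Four are numbers of events: "No. of intradialytic hypotensive episodes", the matching items for hypertension and new arrhythmia, and "No. of episodes of stopping CKRT due to filter clotting or clogging".

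SAP 5.2.2 adjudicates safety outcomes from the start of the intervention to 12 h after CKRT ends. Protocol Appendix F1 collects several of them up to 24 h after CKRT ends.

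The analysis is described in three places:
- SAP 4.3, which covers secondary and safety outcomes: "For continuous variables, we will report incident rate ratios calculated with zero-truncated negative binomial regression modeling adjusted for prespecified baseline covariates".
- SAP Appendix A codes the four outcomes as continuous, analysed by GLMM. It gives no distribution, link or offset.
- SAP Table 3 has columns for patients (%) and for episodes, but its footnote reads "P values are for the between-group differences in the percentage of patients with a specific event".

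None of the three names hours on CKRT, person-time or an offset. For protocol deviations, SAP 4.2.2 does plan a time-based summary, "no. of occurrences of deviations for six consecutive hours divided by" the days of net ultrafiltration. Protocol Appendix F2 collects "Hours of therapy" on study days. Duration of KRT is a secondary outcome (SAP 3.5.2).

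**The concern.** An episode can be counted only while the patient is under observation, and here the length of observation follows the patient's own time on CKRT. The strategy under test may change that time. A bare count therefore mixes two things: how risky an hour of treatment is, and how many hours there were. The central hypothesis (Protocol 3, SAP 3) is that the restrictive strategy brings fewer complications, hypotension and arrhythmia among them, so readers will want to tell the two apart.

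The three descriptions also allow different P values for one outcome, with no rule for which is reported. SAP 4.3 sets the threshold for all of them: "We will consider observed differences between groups to be statistically significant at a two-sided, nominal alpha of 0.05 for all outcomes". The results have a use during the trial as well. Under Protocol 13.3.2 the DSMB reviews the frequency of hypotension by group, and a finding that adverse events are more frequent in one group must be passed to the IRB.

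**Working it through.** The documents give no figure for this comparison, so there is none to reproduce.

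**Inputs**
- Liberal CKRT time: 96 h, from the four-day average in Protocol 5.2.8. Using it as the liberal-arm mean is an assumption.
- Tail: 12 h (SAP 5.2.2), or 24 h (Protocol Appendix F1).
- Liberal patients with at least one event: 43%, after the 43.2% with hypotension in an earlier trial's cohort (Protocol 5.2.5). Illustrative only.
- k, restrictive CKRT time divided by liberal CKRT time: not in the documents. Assumed range 0.75 to 2.
- The same constant hourly risk in both arms, so the true rate ratio is 1.

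**Formulas**
- Count ratio = (96k + tail) / (96 + tail)
- Restrictive patients with an event = 1 − (1 − 0.43)^(count ratio)

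**Results**

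| k | Count ratio, 12 h tail | Count ratio, 24 h tail | Patients with an event, restrictive v liberal (12 h tail) |
|---|---|---|---|
| 0.75 | 84/108 = 0.78 | 96/120 = 0.80 | 35.4% v 43.0% |
| 1 | 1.00 | 1.00 | 43.0% v 43.0% |
| 1.25 | 132/108 = 1.22 | 144/120 = 1.20 | 49.7% v 43.0% |
| 1.5 | 156/108 = 1.44 | 168/120 = 1.40 | 55.6% v 43.0% |
| 2 | 204/108 = 1.89 | 216/120 = 1.80 | 65.4% v 43.0% |

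The last column shows that the quantity tested in Table 3 depends on exposure too, so moving to percentages does not remove the problem.

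**Zero truncation.** A zero-truncated model is fitted only to patients with at least one episode. If 43.2% have hypotension, 56.8% leave the analysis: about 41 of 72 per group (SAP 3.6) or 32 of 56 (Protocol 9.1).

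**Simulated false-positive rate at nominal 5%.** Each setting had 400 runs, gamma-distributed CKRT time with mean 96 h in the liberal arm, a 12 h tail, 0.012 episodes per hour with gamma frailty (mean 1, variance 1), and no clustering or period effects. The table shows k = 1.5.

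| Analysis | 72 per group | 56 per group |
|---|---|---|
| Negative binomial, no offset | 40.7% | 24.0% |
| Zero-truncated negative binomial, no offset | 24.2% | 18.0% |
| Percentage of patients (chi-square) | 18.5% | 10.2% |
| Negative binomial, log(hours) offset | 5.8% | 5.8% |

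At k = 1 every analysis stays between 4.5% and 6.8%. With the offset, the median rate ratio is 0.98 to 1.03 and rejection is 4.5% to 6.0% at every k from 1 to 2. The rates and frailty are assumed, so only the pattern should be relied on.

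**The case against.** **Total episodes per patient is a legitimate outcome.** Under intention to treat, if a strategy lengthens CKRT and so exposes patients to more episodes, that is a real effect, and an offset based on post-randomisation hours would hide it. This stands. It is a reason to keep the total count beside the rate, but the total alone cannot show whether an hour of treatment is safer.

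**A rate ratio is already planned.** SAP 4.3 speaks of incident rate ratios from a negative binomial model, which may imply an exposure term. That is fair as far as the model family goes. The exposure is never stated, however, and the zero truncation does not suit event counts that can be zero.

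**The deviation contrast is limited.** The per-day figure in SAP 4.2.2 is one of three descriptive summaries; the test there compares proportions of patients. The contrast shows only that a time denominator was within the authors' reach.

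**The consequence is modest.** Protocol 11.3 says the trial is not powered for adverse events. Table 3 shows patients and episodes, its footnote says what is tested, and Table 2 reports KRT duration by arm. All this limits the harm, but leaves the reader to combine the pieces.

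**Risk may not be constant.** Protocol 5.2.5 reports hypotension within the first hour in 43% of patients. If risk is front-loaded, extra hours add less and the count ratios lie nearer 1. For the same reason, an hourly rate can flatter the arm with longer treatment, which is another reason to show both summaries.

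**Conclusion.** The point holds for the missing denominator and the conflicting analyses. At equal hourly risk, the four counts and the percentages derived from them are distorted against whichever arm spends longer on CKRT. The illustrative count ratio runs from 0.78 to 1.89 for k from 0.75 to 2, and there is no distortion at k = 1. This rests on a 96 h base, a 12 h tail and constant hourly risk.

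A reader might infer that the restrictive arm will look more harmful, with a ratio that follows the removal rates: 1.53 at the minimum separation (1.0 v 1.53 mL/kg/h), or 3.5 at mid-range values (1.0 v 3.5). The documents do not support this:
- Protocol 5.3.2 says only that slower removal "may increase time to achieving euvolemia", and presents this as theoretical.
- Protocol 5.2.1 reports longer KRT dependence at rates above 1.75 mL/kg/h.
- Protocol 5.3.1 expects fewer interruptions and fluid boluses with restrictive removal.
- The consent items in Protocol 12.3 leave open whether dialysis time will be longer or shorter.
- Protocol treatment also ends with transfer to IHD, withdrawal of life support, death or day 28 (Protocol 7.3), so CKRT time need not scale with removal rate.
- No document expects a liberal mean of 3.5. That arm starts at 0.5 and rises as tolerated (Protocol 7.2).

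Because the direction is unknown, the denominator should be fixed before the data are seen.

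**What to change.** For hypotension, hypertension, arrhythmia and clotting:

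1. In SAP 4.3 and Appendix A, specify a negative binomial mixed model without zero truncation, with log(hours at risk) as offset.
2. Define hours at risk to match the adjudication window: either CKRT hours plus the stated tail, or CKRT hours alone with events restricted to time on CKRT. Reconcile the 12 h (SAP 5.2.2) and 24 h (Protocol Appendix F1) tails first.
3. In Table 3, report episodes per 24 h at risk, the rate ratio with 95% CI, and that model's P value.
4. Keep total episodes per patient and the percentage of patients with an event as burden summaries.
5. Reword the Table 3 footnote so that each P value is labelled by the quantity it tests.

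The cost is SAP wording; CKRT hours are already on the data schedule. The downside is two kinds of summary per outcome. The rate also conditions on exposure that arises after randomisation, so it must be read beside the total count and cannot replace it.

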### 3.6 SAMPLE SIZE AND MONITORING

1. Using the sample size calculation for stepped wedge cluster randomized trial (SW-CRT) design, 126 patients will have 80% power at a two-sided alpha of 0.05 to reject the null hypothesis that the average  $UF_{NET}$  rate was at least 0.52 mL/kg/h different between the two groups, using intra-cluster correlation coefficient of 0.01, at a standard deviation of 0.75, and assuming mean  $UF_{NET}$  rate of 1.0 mL/kg/h. After accounting for a potential 10% attrition rate, the sample size was increased to 144 subjects or 72 patients per group.
2. The principal analysis will be intent-to-treat based upon randomization assignment.
3. The trial progress will be evaluated by an independent Data and Safety Monitoring Board (DSMB). Being a feasibility study there will be no interim analyses.

## 4 DATA ANALYSIS PLAN

### 4.1 OVERALL ANALYTICAL PLAN

All analyses will be performed on an intention-to-treat basis, which generally biases toward no difference. We will also perform per-protocol analyses where the assigned intervention was followed. We will first examine the data structure, distributions of the outcomes and explanatory variables, and potential missing data elements. Missing data will be imputed after examining the reason for missingness. For data that are missing completely at random or missing related to other collected covariates, we will use the multivariable imputation by chained equation (MICE) to impute data before fitting models.

The individual ICU is the unit of randomization, and the individual patient is the unit of analysis. In SW-CRT, the usual comparisons between two treatments need to be made over a differing time making standard group comparison-based methods biased and potentially ineffective. Therefore, we will use adjusted generalized linear mixed models (GLMM) for all primary and secondary outcomes, as delineated by Hussey and Hughes and others, to account for temporal and clustering effects typically encountered in SW-CRT designs. In these models, we will use the ICU as random effects. Time will be treated as random in the main analysis but will also be treated as fixed effects and interact with other covariates.

We will adjust all analyses for prespecified variables such as age, baseline eGFR, severity of illness as measured by the acute physiology and chronic health evaluation (APACHE)-III score, Elixhauser Comorbidity Index score, use or nonuse of mechanical ventilation, admission source, percentage of fluid overload before study enrollment, presence or absence of sepsis, baseline cardiovascular SOFA score and any other variable that are associated with outcome of  $UF_{NET}$  and had a between-group difference ( $P \leq 0.2$ ) on univariable analysis. We will assess the stability of final models using routine model diagnostics to identify potential outliers and/or influential observations. We will report both

adjusted and unadjusted analyses stratified by restrictive and liberal UFNET groups.

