#### 4.2.3 RECRUITMENT RATE

A successful recruitment rate will be defined as achieving an enrollment rate of 2 patients per month per center during the trial. The recruitment metric will be calculated as the mean number (standard deviation) of recruited patients per active screening month.

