## 5 APPENDICES

### 5.1 APPENDIX A: OUTCOME VARIABLES AND ANALYSIS METHOD

Variable	Outcome Category	Scale	Analysis Method
Between-group separation in mean delivered UF NET rates	Primary	Continuous	GLMM
Protocol deviation	Primary	Binary	Wald-test for GLMM
Recruitment rate	Primary	Continuous	GLMM
Daily fluid balance	Secondary	Continuous	GLMM
Cumulative fluid balance	Secondary	Continuous	GLMM
Duration of kidney replacement therapy	Secondary	Continuous	GLMM
Duration of mechanical ventilation	Secondary	Continuous	GLMM
Organ failure free days	Secondary	Continuous	GLMM
ICU length of stay	Secondary	Continuous	GLMM
Hospital length of stay	Secondary	Continuous	GLMM
Hospital mortality	Secondary	Binary	Wald-test for GLMM
Dialysis dependence at hospital discharge	Secondary	Binary	Wald-test for GLMM
Hypotensive episodes	Safety	Continuous	GLMM
Hypertensive episodes	Safety	Continuous	GLMM
Cardiac arrhythmias	Safety	Continuous	GLMM
Emergent use of rescue UF NET rates	Safety	Binary	Wald-test for GLMM
Severe hypophosphatemia	Safety	Binary	Wald-test for GLMM
Severe hypokalemia	Safety	Binary	Wald-test for GLMM
Severe hypocalcemia	Safety	Binary	Wald-test for GLMM
CKRT stopping due to hemofilter clotting or clogging	Safety	Continuous	GLMM
Discontinuation of fluid removal due to hemodynamic instability	Safety	Binary	Wald-test for GLMM
Inability to close surgical wounds	Safety	Binary	Wald-test for GLMM
New organ dysfunction	Safety	Binary	Wald-test for GLMM
Worsening systolic/diastolic cardiac function	Safety	Binary	Wald-test for GLMM

Worsening pulmonary edema	Safety	Binary	Wald-test for GLMM
Worsening of ileus	Safety	Binary	Wald-test for GLMM
Bowel ischemia or anastomotic breakdown	Safety	Binary	Wald-test for GLMM
Pressure ulcerations	Safety	Binary	Wald-test for GLMM
New wound infections	Safety	Binary	Wald-test for GLMM
New arterial or venous thrombosis	Safety	Binary	Wald-test for GLMM
Severe anemia	Safety	Binary	Wald-test for GLMM
Severe thrombocytopenia	Safety	Binary	Wald-test for GLMM
New secondary infections	Safety	Binary	Wald-test for GLMM

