5.3.2 TABLE 2: PRIMARY AND SECONDARY OUTCOMES

	Outcomes	Unadjusted Analysis			Adjusted Analysis		
		Restrictive (N= XX)	Liberal (N=XX)	P value	Restrictive (N= XX)	Liberal (N=XX)	Estimated Effect of Intervention (95% CI)
Primary							
Delivered UF NET rate, mean (SD)							
Delivered UF NET rate, median (IQR)							
No. of participants with protocol deviation							
Recruitment rate per month per site							
Secondary							
Daily fluid balance excluding UF, mL, median (IQR)							
Cumulative fluid balance excluding UF, mL, median (IQR)							
Daily fluid balance including UF volume, mL, median (IQR)							
Cumulative fluid balance including UF volume, mL, median (IQR)							
Duration of kidney replacement therapy, days, median (IQR)							
Duration of mechanical ventilation, days, median (IQR)							
Organ failure free days, days, median (IQR)							
ICU length of stay, days, median (IQR)							
Hospital length of stay, days, median (IQR)							

	Outcomes	Unadjusted Analysis			Adjusted Analysis		
		Restrictive (N= XX)	Liberal (N=XX)	P value	Restrictive (N= XX)	Liberal (N=XX)	Estimated Effect of Intervention (95% CI)
	Kidney replacement therapy dependence at discharge among survivors						
	Hospital mortality						

\$ Adjusted for differences in age, baseline eGFR, APACHE-III score, Elixhauser Comorbidity Index score, mechanical ventilation, admission source, percentage of fluid overload, sepsis, and baseline cardiovascular SOFA score.

[figure not shown]

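### Recruitment, a primary outcome, is assigned a patient-level adjusted GLMM that cannot be applied to it and that conflicts with the SAP's own recruitment section

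*SAP*

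**What the plan says.** Three places in the SAP point to a modelled comparison of arms.

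- **SAP 4.1** says "we will use adjusted generalized linear mixed models (GLMM) for all primary and secondary outcomes", that "the individual patient is the unit of analysis", and "We will adjust all analyses for prespecified variables such as age, baseline eGFR, severity of illness", followed by further patient-level variables. On clustering it says "In these models, we will use the ICU as random effects".
- **SAP Appendix A (5.1)** has a separate row for this outcome: "Recruitment rate Primary Continuous GLMM".
- **SAP shell Table 2 (5.3.2)** lists "Recruitment rate per month per site" among the primary outcomes. The column headings are restrictive and liberal, an unadjusted P value, and an adjusted effect with 95% CI.

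The section written for the outcome says something else. **SAP 4.2.3** sets a target of 2 patients per month per center and continues: "The recruitment metric will be calculated as the mean number (standard deviation) of recruited patients per active screening month". It names no model, arm or covariate. **Protocol 5.8.1** uses the same descriptive mean (SD), interpreted at the end of the trial, but sets the target at 1 patient per ICU per time window.

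**The concern.** The trial is meant to show whether a larger one is feasible, and recruitment is one of its three primary feasibility outcomes. An analyst following the SAP finds two incompatible instructions for it. One is a covariate-adjusted model on patient data, comparing restrictive with liberal. The other is a single descriptive rate set against a target.

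The first cannot be carried out as described. The second can, but it gives no interval. The SD of monthly counts describes how much months vary, not how precisely the rate is known. With about one recruit expected per ICU per window, that precision matters to the conclusion. If the conflict stays open, the method for a primary outcome will be chosen after the counts are known.

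**Working it through.** **Step 1. Can the assigned model be applied to recruitment?** Taking its elements in turn:

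| Element in 4.1, Appendix A or Table 2 | Applied to recruitment |
|---|---|
| Unit: the patient | A patient has no recruitment count; the outcome belongs to an ICU (or center) and a period |
| Covariates: age, eGFR, severity and others | These exist only for enrolled patients; a period with no recruits has none |
| Scale: Continuous | The data are counts over screening time |
| Restrictive versus liberal, per month per site | ICUs cross over one at a time (Protocol 6.3.2), so during rollout one site can hold ICUs of both arms in the same month, and that site-month belongs to neither arm |

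The ICU random effect and the time terms would suit recruitment. The unit, covariates, scale and arm display do not.

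**Step 2. The plan's own accrual figure.** Protocol 9.1 gives 10 ICUs, 24 months, and a minimum of 0.93 patients per ICU per 2 months.

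- Windows per ICU: 24 / 2 = 12. ICU-windows: 10 × 12 = 120.
- Expected recruits: 0.93 × 120 = 111.6. The Protocol states 111, so the figure reproduces.

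**Step 3. The rate with an interval.** Take the planned maximum of 112 recruits (Protocol 6.1). Assume 120 fixed ICU-windows and Poisson counts.

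- Rate: 112 / 120 = 0.93 per ICU-window.
- Exact Poisson lower limit for the count: χ²(0.025; 2 × 112) / 2 = 92.2. Divided by 120, this is 0.77.
- Exact Poisson upper limit: χ²(0.975; 2 × 113) / 2 = 134.8. Divided by 120, this is 1.12.

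The point estimate is below the Protocol's target of 1, and the interval includes 1.

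**Step 4. The same recruitment against the two stated targets.**

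- Protocol target, 1 per ICU per window: 112 / 120 = 0.93, not met on the point estimate.
- SAP target, 2 per month per center: 112 / (2 centers × 24 months) = 2.33, met.

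One result therefore fails in one document and succeeds in the other. Reaching the Protocol's target over all 120 windows would take 1 × 120 = 120 recruits, more than the planned maximum of 112.

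**The case against.** The best defence is that 4.2.3 is the specific section and governs, and that 4.1 is general text never meant to reach recruitment. Table 2 is an empty shell with one set of headings for every row, so those cells may never have been meant to be filled. Poisson and negative binomial mixed models are themselves GLMMs, and the row label in Table 2 suggests aggregate counts. A point estimate compared with a threshold is also an acceptable feasibility rule.

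Much of this stands. The success verdict most plausibly comes from 4.2.3, and a count GLMM on ICU-period data can be fitted. It would be wrong to say that no GLMM could be used. An interval is a refinement of the decision rule rather than a condition for having one. The defence does not account for Appendix A, which gives recruitment its own row and calls it Continuous with GLMM. Nor does it remove the statements in 4.1 that the patient is the unit and that all analyses are adjusted.

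A reader might go further and infer that the SAP discards periods with no recruits, so that the rate is biased upward and failed recruitment could be declared a success. The documents do not support this. Nothing in them excludes empty periods, and a denominator of active screening months would naturally keep them. The loss would occur only if the analysis were built from patient rows. Nor does dropping empty periods guarantee a false pass. Suppose a true rate of 0.6 per two-month ICU-window and 5 ICUs per center. That is 0.6 × 5 / 2 = 1.5 per center-month. Averaging only the non-empty months under Poisson counts gives 1.5 / (1 − exp(−1.5)) = 1.93, still under the SAP's target of 2.

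**Conclusion.** The concern holds as a defect of specification. SAP 4.1, Appendix A and Table 2 give a primary outcome an analysis that cannot be applied to it as described, and they conflict with SAP 4.2.3 and Protocol 5.8.1. The documents do not show that the recruitment result will be biased, and no size of bias is claimed.

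The practical size lies in the precision and the criterion. At the planned total the rate is 0.93 per ICU-window (95% CI 0.77 to 1.12), which does not settle whether the Protocol's target of 1 was reached. The same total passes the SAP's target at 2.33 per month per center.

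These figures assume 120 fixed windows, Poisson counts and enrollment spread over the full 24 months. The documents give no count distribution, and a window can close early once 10 patients are enrolled. The simple interval also ignores variation between the 10 ICUs; allowing for it would probably widen the interval. The trial design is unaffected.

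**What to change.** In the SAP:

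1. Exempt recruitment from the adjusted GLMM in 4.1, change its row in Appendix A, and mark the P-value and adjusted columns of Table 2 as not applicable for it.
2. Make the rate in 4.2.3 the governing analysis. Compute it from counts per ICU and period over all active screening time, and state that periods with zero recruits are included.
3. Report the rate with a 95% CI beside the SD. A Poisson or negative binomial model with active screening time as offset and allowance for ICU would serve, with no patient covariates. An offset also handles windows of unequal length.
4. Give by-arm rates as description only, assigned by ICU and period rather than by site-month.
5. Reconcile the SAP's target (2 per month per center) with the Protocol's (1 per ICU per time window), and name one criterion and whether the point estimate or the interval decides.

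The cost is mostly wording. The one data requirement is active screening time for each ICU. The screening log described in Protocol 6.7 and Appendix C is kept per patient, so that time has to be recorded separately if it is not already. The 4.2.3 metric needs a screening-time denominator in any case.
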